|   | 
 
• Willing and able to consent to participate (written, informed consent);
 
• Willing and able to attend/complete the requested follow-up visits;
 
• Considered for treatment with one or more approved or cleared Wright Medical products included in this study
 
  |
| Exclusion Criteria                                   | Subjects will be excluded from the study if they meet any of the following criteria: 
 
• Subjects determined, by the investigator, to be an inappropriate candidate for the procedure indicated;
 
• Unable to consent to participate (written, informed consent);
 
• Unable to attend/complete the requested follow-up visits
 
 |
| Visit Schedule                                       | Pre-op/Op, and Last scheduled standard of care and/or surgeon release follow-up (FU) time point. Additionally, PROMS and safety may be followed yearly to sufficiently assess the safety of the product throughout the defined product clinical lifetime as needed based on the current risk analysis for the product.  |
| Statistical Methods                                  | Descriptive statistics, Kaplan Meier survival analysis and Life tables  |
| Duration of Clinical Investigation                   | Expected enrollment is 5 years
Based on varied definitions of product clinical lifetime, the follow-up period will be 12wks to 10 years  |
| Number of Sites and Subjects                         | $n =$ a minimum of 40 patients per device or until sufficient data is collected to satisfy the notified bodies
5 to 15 sites   |
| Committees (e.g., safety, steering) and/or Core Labs | none  |

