**6.2.2 Criteria and Procedures for Subject Withdrawal or Discontinuation**

Subjects maintain the right to discontinue their participation in the study at any point without penalty or loss of benefit to which the subject is otherwise entitled per ICH E6 4.8.10(m) guidelines. If at any time the study device is removed, the subject will be discontinued from the study unless the subject has other study devices remaining.

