### **7.3 Data Analysis**

Improvements in subject quality of life after surgery will be assessed by constructing 95% confidence interval for the mean change from baseline score in EQ-5D-5L and FAMM total and component scores.

|   |  |  |
|---|--|--|
|  | Clinical Investigation Plan
Foot and Ankle Products | CIP- INT19-MDR-001
Version: 2 |
|---|--|--|

Survivorship of a Wright product will be assessed based on adverse event resulting from the presence or performance of the device. The Kaplan Meier survivorship method and life table analysis will be employed. Time to adverse event due to the presence or performance of the implant will be the survivorship endpoint for each Wright device. Also, time to reoperation to exchange or remove any part of the Wright device due to failure of the implant will also determine the Wright product survivorship. Subjects who will not experience these events will be censored at the last follow-up visit. The Kaplan Meier survival curve and the 95% Confidence Interval will be constructed.

Safety endpoints will include all adverse events (AE), serious AE (SAE), unanticipated adverse device effects (UADEs).

All subjects enrolled in the study will be assessed for safety. Adverse events and other safety evaluations will be reported as frequency and rates as appropriate, cumulative over the different follow-up schedules.

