##### **11.4.2 Sponsor Reporting**

**Recording and Reporting Adverse Events - Wright Medical Responsibilities**  
Wright Medical is responsible for the classification of AEs and ongoing safety evaluation of the study and will:

- Review the Investigator's assessment of all AEs; determine and document, in writing, the seriousness of the adverse event and relationship of the adverse event to the implanted components.

In case of a disagreement between Wright Medical and the Investigator, Wright Medical shall:

- Communicate both opinions to concerned parties; and
- As required, ensure that the IRB/EC/REC and regulatory authorities are informed of significant new information involving the product during the study
- Or seek independent review as needed.

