Whenever the available data allows, the standard deviation, interquartile range (IQR) and maximum and minimum will be calculated. All quantitative variables will be assessed for normality via the Shapiro-Wilk test. The 95% confidence interval (CI) of the mean will be presented when the normality of the data is met.

All qualitative variables, including those based on summaries (secondary elements), will be analyzed listing the proportions, frequencies, column and row totals and missing proportion (if any).

The proportion of device surviving at each visit will be summarized for each device. Rates will be computed based on available data. Missing data will not be imputed.

No imputations for missing data will be conducted.

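### The SAP text describes device survivorship only as a per-visit proportion and leaves its listed life tables unspecified, so the protocol's censoring rule and survival confidence interval are not carried over

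*SAP*

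**What the plan says.** **Protocol.** Section 7.3 sets out survivorship device by device. The first event is plain: "Time to adverse event due to the presence or performance of the implant will be the survivorship endpoint for each Wright device". A second is added as also determining survivorship: "time to reoperation to exchange or remove any part of the Wright device due to failure of the implant". On censoring it says: "Subjects who will not experience these events will be censored at the last follow-up visit". On precision: "The Kaplan Meier survival curve and the 95% Confidence Interval will be constructed". The synopsis gives the same commitment under Statistical Methods: "Descriptive statistics, Kaplan Meier survival analysis and Life tables".

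**SAP.** Section 3.1 says: "The proportion of device surviving at each visit will be summarized for each device. Rates will be computed based on available data", with no imputation. Section 6.6 makes device-failure rates the basis of the survival rates. Appendix 2A lists three by-device life tables: first device-related adverse event, device failure, and death. Nothing in the SAP body describes them, and the templates in Appendix 2B include none of them. The supplied SAP text does not mention Kaplan-Meier, censoring or an interval for survival. The interval rule in section 3.1 concerns means of normally distributed variables. Section 4.8 refers time calculations to the analysis chapter, which names no start or end date for survival.

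**The concern.** A programmer working from the SAP has one written rule, a proportion at each visit, and some table titles with no event definition, censoring rule or interval method behind them. The written rule does not give survival at a defined time after surgery, and it leaves the denominator open.

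Three features of the study make this matter:

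- **Visit timing.** SAP Table 4.4.1 allows the final clinical visit at any time from operation to 1 year, and yearly visits a window of one year either side.
- **Exit on removal.** Under Protocol 6.2.2, if a study device is removed, "the subject will be discontinued from the study unless the subject has other study devices remaining". A failed device can therefore leave the set of patients seen at later visits.
- **Small groups.** SAP 3.1 summarises any device implanted in at least 10 patients, where a bare percentage says little.

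The study exists to supply device safety and performance evidence under the EU device regulation. Per-device survivorship is part of what the protocol promised for that purpose.

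**Working it through.** The documents state no survivorship rate, event count or precision target, so there is no figure of the plan's own to reproduce. The only sample size concerns EQ-5D precision: (1.96 × 0.313 / 0.1)² = 37.6, so n = 38, as stated. It says nothing about survivorship.

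**1. Element by element**

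| Element | Protocol 7.3 | SAP |
|---|---|---|
| Estimator | Kaplan-Meier and life table | Per-visit proportion in 3.1; life tables by title only in Appendix 2A |
| Events | Device-related adverse event; reoperation for implant failure | Device failure in 6.6; life-table titles for first device-related adverse event, device failure and death |
| Censoring | Last follow-up visit | None stated |
| 95% interval | Yes | None for survival |
| Time origin | Not explicit | Not explicit |

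The censoring rule and the interval are lost between the documents. The missing time origin is common to both.

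**2. Visit windows.** A 1-year visit with a window of one year either side can fall at 0 to 2 years, and a 2-year visit at 1 to 3 years. The windows overlap for the 5 of 43 devices in SAP Appendix 1 that are followed beyond 1 year. To show the effect, assume a constant hazard, so S(t) = S(1)^t, and use only half the window (0.5 to 1.5 years):

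- 1-year failure 5%: 0.95^0.5 = 97.5%; 0.95^1.5 = 92.6%
- 10%: 0.90^0.5 = 94.9%; 0.90^1.5 = 85.4%
- 20%: 0.80^0.5 = 89.4%; 0.80^1.5 = 71.6%

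**3. Denominator and order of events.** Assume 10 implanted and 3 lost event-free at 6 months, and estimate 12-month survival. The two crude readings shown both keep recorded failures, as SAP 6.6 tabulates them.

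| Failures | Kaplan-Meier | All implanted | Losses dropped |
|---|---|---|---|
| One at 3 months | 9/10 = 90.0% | 9/10 = 90.0% | 6/7 = 85.7% |
| One at 9 months | 6/7 = 85.7% | 9/10 = 90.0% | 6/7 = 85.7% |
| One at each time | (9/10) × (5/6) = 75.0% | 8/10 = 80.0% | 5/7 = 71.4% |

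The crude figures differ from Kaplan-Meier by 0 to 5 points, in either direction. If only attendees were counted, each row would read 100% (6/6, 6/6, 5/5), because the failures have left the denominator. The SAP does not state that reading, but its wording does not exclude it.

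For the last row, the Greenwood sum is 1/(10 × 9) + 1/(6 × 5) = 0.0444, the standard error is 0.75 × √0.0444 = 0.158, and the log-log 95% interval is 29.8% to 93.4%.

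**4. Precision at the reporting threshold.** Clopper-Pearson 95% intervals for survival with 10 patients and complete follow-up:

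- 0 failures: 69.2% to 100%
- 1 failure: 55.5% to 99.7%
- 2 failures: 44.4% to 97.5%

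**The case against.** The best defence is that nothing has been withdrawn. The SAP is tied to protocol Version 2 on its front page, two of its listed life tables correspond closely to the protocol's two events, and the usual output of a life table is a proportion surviving at successive intervals. The sentence in SAP 3.1 may be loose shorthand for those tables. Survivorship is also not a named endpoint in Protocol 5.4, and SAP 3.1 makes every analysis descriptive.

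Much of this stands. A reader might infer that the SAP has abandoned Kaplan-Meier; the listed life tables do not support that. A reader might also treat the missing time origin as the SAP's omission, but Protocol 7.3 does not state one either. The descriptive purpose is no reason to leave the method out, since Kaplan-Meier is itself descriptive. And if the sentence is shorthand, no SAP text says so or supplies the rules the tables need.

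Two further readings go too far. One is that a crude rate always overstates survival; the examples show that it can match Kaplan-Meier, exceed it or fall below it. The other is that the SAP counts each event under every device a patient received. SAP 3.1 enters patient-level data under each device but gives no rule for events, and the adverse event template tabulates device-related events and failures by device. Double counting is possible, not stated.

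**Conclusion.** The point holds as a gap in specification that should be fixed. The SAP neither carries over the protocol's censoring rule and survival interval nor specifies the life tables it lists, and the one rule it does write down gives a figure that is not survival at a defined time.

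The size in this study cannot be determined. The failure counts, losses, hazards and half-window above are assumptions. In the 10-patient example the shift from Kaplan-Meier, with recorded failures kept, is at most 5 points and lies well inside the interval. The undefined time and the missing interval are therefore the larger problems. Confidence in the missing specification is high.

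The comparison is with protocol Version 2, the version supplied. The figures appendix mentioned in SAP section 7 is not in the supplied text, so nothing is claimed about whether a survival curve is planned.

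**What to change.** In SAP 3.1 and 6.6, replace the per-visit proportion with the Protocol 7.3 analysis:

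- For each reported device, give Kaplan-Meier and life-table estimates from the date of surgery, censored at last follow-up, with 95% intervals, at stated times after surgery.
- State whether device-related adverse event and reoperation for implant failure are two endpoints or one composite; Protocol 7.3 can be read either way.
- Count a removal for implant failure as an event even if the subject then exits under Protocol 6.2.2.
- Link the life tables listed as Tables 5.1 and 5.2 to this analysis and supply templates for them.
- State that device-related events and failures are assigned to the device concerned. Protocol 11.4.2 already has the sponsor "determine and document, in writing, the seriousness of the adverse event and relationship of the adverse event to the implanted components", which provides the basis.

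The cost is minor SAP wording, some programming and some event attribution. Operation date (Protocol 6.3.5.2) and event onset date (Protocol 11.3) are already collected. The intervals will be wide for devices with about 10 patients, which is what the data can support.

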### 3.1.1. Primary Analysis / Endpoint

Improvements in subject quality of life after surgery will be assessed by constructing 95% confidence interval for the mean change from baseline score in EQ-5D-5L.

### 3.1.2. Secondary Analyses

FAAM score improvements from baseline will be summarized with 95% confidence interval for the mean.

Safety of Wright medical products will be assessed by the frequency and rates of the with collected AE safety profiles.

Surgeon and patient assessment of Wright devices will be presented descriptively.

### 3.1.3. Additional Analyses

Additional Analyses are outlined in the subsequent sections. Analysis details (variables, level of measurement, planned steps) are listed in-depth in the SAP.

- Fusion/Consolidation time for applicable devices
- Deformity Correction for applicable devices

## 4. Methods

### 4.1. RANDOMIZATION

No randomization was implemented in the study. A consecutive series of subjects at each site meeting all the eligibility criteria will be enrolled in this clinical investigation.

### 4.2. STATISTICAL INTERIM ANALYSES AND STOPPING GUIDANCE

Interim analyses will be performed on an annual basis. The progress of the clinical investigation will be reported together with the interim results on the variable level according to the analysis plan.

There will be no stopping rules specified for this clinical investigation.

### 4.3. TIMING OF FINAL ANALYSES

The full final report with complete analyses, progress and conduct reporting will be created at the end of this clinical investigation.

### 4.4. TIMING OF OUTCOME ASSESSMENT

Data will be collected at baseline, surgery, at last scheduled standard of care and/or surgeon release FU time point. Additionally, PROMs and safety may be followed yearly to sufficiently assess the product over the clinical lifetime as needed based on the current risk analysis for the product.

The follow-up evaluations will include assessment of device-related adverse events/incidents, evaluation per EQ-5D-5L and FAAM scores as well as surgeon surveys. See the section below for visit windows and a list of assessments to be performed at each visit, given by the CIP.

Table 4.4.1: Assessments and Clinical Investigation Elements

Procedures	Pre-op/ Op	Final Clinical Follow-Up Visit (Op to 1yr)	1-10 yr (-/+1 yr) (yearly as necessary) 	Study Close
Informed Consent	X			
Inclusion/Exclusion Criteria	X			
Medical History/Demographics	X			
Operative (Surgical) procedure/device	X			
EQ-5D	X	X	X	
FAAM	X	X	X	
Surgeon Survey with radiographic assessment		X		
Adverse Event Assessment	X	X	X 	
Patient Survey			X	
End of Study				X
Surgical Intervention 				
*Sponsor-approved Unscheduled Visit 				

1&2 These are not scheduled time point events but will be observed throughout study participation

 Only required when patient survey indicates an adverse event occurred

 Follow-up time points only executed if needed per device clinical lifetime definition

#### 4.5. STATISTICAL SOFTWARE

All statistical analyses will be performed using SAS Version 9.4 or higher on a SAS PC platform.

#### 4.6. MISSING DATA

The intent is to collect as complete a dataset as possible. Nevertheless, in some situations missing data cannot be avoided. The reports and tables therefore will show the number and percentage of missing cases for each analyzed variable in relation to the enrolled cases for each post-operative assessment.

Missing data will be reported for each variable or calculation (if any) and overall totals will be reported including the proportion of missing data (if any).

#### 4.7. UNITS

See analysis chapter for details related to units used for the different variables and calculations. In case of collection of variables with non-SI units (i.e., pounds instead to kilograms), conversion of such data into SI units (and vice versa) will be ensured and both results will be reported for the full set of available subjects next to each other in the interim/annual and/or final reports.

#### 4.8. CALCULATIONS AND TRANSFORMATIONS

Distances between times and differences between score results will be calculated. For full details of variables used for calculations and the creation of new variables based on these calculations, see analysis chapter.

### 5. Population and Progress

All analysis will include all subjects implanted with any of the Wright devices listed in Appendix 1, hence called Treated population.

### 6. Analysis

This section will contain the instructions for data analysis and table templates of the presentation of statistical analysis results. The components of the table template will guide the statistical programming and report generation.

#### 6.1. Patient Accounting

See [Table 1.1](#). A summary of subject disposition will be made, noting the number who attended the baseline visit, had the surgery visit by Wright device implanted/used, and then subsequently attended the remaining study visits.

#### 6.2. Baseline Characteristics

##### **Subject eligibility**

See [Table 1.2](#). The inclusion and exclusion criteria will be summarized for the treated population in order to assess adherence or deviation of subjects to the study eligibility.

##### **Demographic**

See [Table 1.3](#). Demographics and clinical characteristics at baseline will be summarized descriptively, and will include the following: Age, Race; Gender; Height in cm; Weight in kg, BMI (kg/m^2) and smoking status. Age in years will be calculated as:

age = FLOOR((INTCK('month',BRTHDT,INFCONDT) - (day(INFCONDT) < day(BRTHDT))) / 12);

##### **Medical Conditions**

See [Table 1.4](#). The pre-operative relevant medical conditions will be summarized by frequency and proportion for each Wright device.

### 6.3. Protocol Deviations

See Table 1.5. Deviations from the protocol that occurred during the conduct recorded for each patient will be summarized by frequency and rate of occurrence.

### 6.4. Intra-operative Factors

See [Table 2.1](#). The operative information will be summarized descriptively and will include the following: indication for use, prior surgery, location of surgery.

### 6.5. Effectiveness

#### 6.5.1. Primary endpoint analysis: EQ-5D

See [Table 3.1](#). EQ-5D is the primary endpoint of the study. EQ-5D is generic health survey that can be used to compare improvement across different interventions and measure changes in health-related quality of life over time. Three language versions of the EQ-5D questionnaire: English, German and France were used. The scores regardless of language will be combined in the analysis. The EQQ-5D Two components of the EQ-5D will be summarized: Index value and overall health score. The five (5) health state measure in the EQ-5D questionnaire will be used to calculate the EQ-5D index value. An EQ-5D for patient standardized for the country origin will be computed based on the total score of the health measures. The country-specific EQ-5D reference scores will be obtained from EuroQoL Group ([www.euroqol.org](http://www.euroqol.org)). A high EQ-5D index value indicates a better health state while a low EQ-5D index value indicates a worse health state. On the other hand, the Eq-5D overall health score, ranges from 0 to 100, is a single measure of the patient's assessment of their current health status. Higher score indicates better health state while a low score indicates a worse health state.

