#### 6.6.2 Secondary endpoints

#### FAAMS

See [Table 3.2.1](#) The Foot and Ankle Ability Measure (FAAM) is a self-report outcome instrument to assess physical function for individuals with foot and ankle related impairments. Like the EQ-5D, three language versions of the FAAM questionnaire were used. The FAAM consists of 29-item questions divided into two subscales: 21-item activities of daily living (ADL) subscale, 8-item sports subscale. Each item is scored on a 5-point Likert scale (4 to 0) from 'no difficulty at all' to 'unable to do'. Responses of "not applicable" are not counted. The score on each of the items are added together to get the subscale total score. The ADL subscale total score range from 0 to 84 and 0 to 32 for the sports subscale. The patient score for the ADL and sports subscale will be transformed to percentage scores by considering the highest possible score for non-missing items. Higher score indicates higher level of function for each subscale, with 100% representing no dysfunction (Martin et al., 2009).

See [Table 3.2.2](#) Patients assessed their current level of function as Normal, Nearly Normal, Abnormal, or Severely Abnormal. Summaries will be presented for each Wright device and visit.

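### SAP 6.5.1 bases the country-standardised EQ-5D index on a total of the five items, and a total does not identify the health state

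*SAP*

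**What the plan says.** The primary analysis in SAP 3.1.1 is a "95% confidence interval for the mean change from baseline score in EQ-5D-5L". SAP 6.5.1 explains what that score is: "Two components of the EQ-5D will be summarized: Index value and overall health score".

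Three consecutive sentences there bear on the index. The first says that the index is derived from the five items of the questionnaire. The second says that a value adjusted to the patient's country is "computed based on the total score of the health measures". The third names EuroQol as the source of the national reference values.

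The second is the only sentence that says how the item responses become a number. Neither document mentions a five-item profile or a profile lookup. The SAP names three language versions of the questionnaire, but no country and no value set. SAP 4.8 (calculations) defers to the analysis chapter, and the Table 3.1 template adds no rule. The protocol (7.3) asks for a confidence interval for mean change and does not describe scoring.

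The SAP shows what it means by a total score in its next subsection, on the FAAM: "The score on each of the items are added together to get the subscale total score".

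**The concern.** The index is one of the two reported components of the primary endpoint, and SAP section 6 is written to guide the programming. A programmer who takes the sentence at face value adds the five item levels and converts the sum to a country-adjusted value. Adding the items discards which dimension is affected and how severely, and a country-specific index needs that information if dimensions or levels differ in weight.

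A second programmer, reading the sentence as loose wording, would score the profile. The two would report different index values, changes and intervals from the same responses. SAP 2.1 says that the results go to regulatory authorities and notified bodies, so the index should be reproducible from the written rule.

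**Working it through.** **1. The plan's own figure.** The disputed sentence contains no number. The figure tied to this endpoint is the sample size (protocol 6.2.6 and 7.2): two-sided alpha 0.05, SD 0.313, half width 0.1.

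n = (1.96 × 0.313 / 0.1)² = 6.135² = 37.6, rounded up to 38.

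The stated 38 reproduces. It depends on the SD and the half width and not on the scoring sentence, so it does not change.

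**2. How much a total retains.** Inputs: five items (SAP 6.5.1) and five levels per item, coded 1 to 5 for counting. The five levels are an assumption from the name EQ-5D-5L.

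- Profiles: 5⁵ = 3,125.
- Totals: 5 to 25, which is 21 values.
- Profiles with total 9 (4 steps above the minimum shared among five items): C(8,4) = 70.
- Profiles with total 15 (10 steps, at most 4 per item): C(14,4) − 5·C(9,4) + 10·C(4,4) = 1,001 − 630 + 10 = 381.
- Only totals 5 and 25 identify one profile. The other 3,123 profiles share 19 totals.

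Within one country, an index computed from the total can therefore take at most 21 values. With three levels per item the result is similar: 3⁵ = 243 profiles and 11 totals.

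Example: 1+1+1+1+5 = 9 and 2+2+2+2+1 = 9. The first has one item at level 5; the second has four items at level 2. The rule cannot separate them.

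**3. When a total would be enough.** Take an index that subtracts a decrement for each item level. Raise one item by one level and lower another by one level: the total is unchanged. The index is unchanged for every such swap only if all one-level steps, on all items, have the same decrement. That is the equal-weight, equal-step case, and the documents do not state it.

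**4. Scale, on assumed weights only.** The documents give no value set. For illustration let

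index = 1 − (1 − v) × Σ wᵢ·g(levelᵢ),

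with v the value of the worst state. Equal steps are g = 0, 0.25, 0.5, 0.75, 1; unequal steps are g = 0, 0.15, 0.25, 0.75, 1.

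| Assumed weights w | Steps | Largest spread within one total, v = 0 | v = −0.3 (×1.3) |
|---|---|---|---|
| 0.2 each | equal | 0 | 0 |
| 0.25, 0.15, 0.15, 0.25, 0.2 | equal | 0.20 | 0.26 |
| 0.2 each | unequal | 0.25 | 0.325 |
| 0.28, 0.12, 0.12, 0.28, 0.2 | unequal | 0.42 | 0.546 |

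Example from the third row, v = 0: 11115 gives 1 − 0.2×1 = 0.80, and 22221 gives 1 − 4×0.2×0.15 = 0.88. In the first row both give 0.80.

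These are differences between individual profiles that share a total. They are not a bias in the mean change, which would depend on the profiles observed.

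**The case against.** The strongest reply is that the sentence is loose wording for the ordinary index. The sentence before it says that the five measures are used, the one after it sends the reader to EuroQol for country scores, and the paragraph is visibly unedited. An experienced programmer might score the profile without pausing. This stands as a limit on certainty: the documents do not show that the index will be computed wrongly. It does not rescue the rule, because the SAP's own use of a total score is a sum and no other text corrects it.

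It can also be said that the analyses are descriptive with no hypothesis test (SAP 3.1), so no decision rule turns on the index, and that the index can be recomputed from the item responses. Both are true. They limit the harm, but the index change and its interval are still primary results.

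Three stronger readings are tempting, and the documents do not support them.

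- **Direction.** A reader might infer that a sum runs opposite to the stated direction, "A high EQ-5D index value indicates a better health state while a low EQ-5D index value indicates a worse health state". The SAP gives no item coding for the EQ-5D, and an index based on a total need not rise with it. No contradiction is shown.
- **Reach.** A reader might infer that all of Table 3.1, or the sample size, is affected. The overall health score is a separate 0 to 100 measure that does not use the five items, and n = 38 does not depend on the scoring sentence.
- **Size.** A reader might take the count of profiles per total as a measure of error. It shows lost information. The error in index units needs a value set, and none is given.

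**Conclusion.** The concern holds in a limited form. As written, the rule does not produce a country-specific EQ-5D-5L index unless every item and every level step has equal weight. It affects the Index Value rows of Table 3.1: the values, their changes from baseline and their 95% confidence intervals.

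The loss of information is 3,125 profiles to 21 totals and rests on five levels per item. The spread within one total is 0 to about 0.55 in the illustrations, but those weights are assumptions, and the effect on the mean change is unknown. The conclusion also rests on reading the total score as a sum, which is how the SAP uses the term for the FAAM. The sentence should be corrected before the final analysis because it governs a component of the primary endpoint.

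**What to change.** Replace the sentence in SAP 6.5.1 with: *The index value is obtained from each patient's five-item health profile (one level per dimension) using a named EuroQol value set specified for each country. It is missing if any dimension is missing, consistent with no imputation. No total of the five items is used.*

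List the countries and the value set chosen for each. The three language versions do not settle this, because the SAP standardises by country and not by language. The missing-item clause applies the no-imputation statement in SAP 3.1 and keeps the FAAM approach, which rescales over the non-missing items, from being carried over.

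The cost is one SAP sentence, a short list of value sets and a check of the derivation code. No new data are needed, and the sample size is unchanged.
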